3.2 Methods

3.1 Overview of Design

This is a pragmatic cluster randomised controlled study. Eligible participating schools will be stratified according to institution type, size, Free School Meal prevalence and local COVID-19 prevalence and randomly allocated into the two study arms. A schematic summarising the study design and participant sub-groups can be found in Figure 2 below.

Regular Active Case Finding. In schools participating in either arm of the study, consent will be obtained from adults/parents/guardians for voluntary weekly testing of all students and biweekly testing of all staff⁵. Tests will be performed with lateral flow devices (LFD)*, and results will be reported in the NHS Test and Trace database. LFD Tests will initially be performed as an assisted test in a school setting. Once a reliable protocol for home testing and recording of LFD is available, schools will be offered the option for at-home self-testing for weekly case finding.

Individuals who test positive will self-isolate and identify first-order contacts according to national guidelines. In addition, symptomatic cases who test positive via NHS Test and Trace, and asymptomatic cases who test positive outside the in-school testing regimen will self-isolate and report their results to the school. All individuals with a positive test will be asked to provide a PCR swab test for genomic sequencing.

1. Intervention (Daily Contact Testing) Arm

a. Public Health Intervention: Consenting first-order contacts of a COVID-positive index case will receive daily contact testing for 7 days from the point of being notified they are a close contact⁶. This will consist of a daily LFD*. Those that receive a negative LFD result can attend school for that day, but other than travelling to and from school will be instructed to continue to self-isolate outside the school setting. Those that receive a positive LFD result should not attend school and will be instructed to self-isolate for 10 days according to national guidelines. The contacts of all first-order contacts (i.e. 'second-order contacts') will be identified to allow the determination of secondary attack rate.

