3.6 Assessment of End-Points

Please see the glossary at the start of this protocol for definitions

Co-Primary End-Points

(i) Number of school days missed among those eligible to be in school.

Daily school attendances will be obtained from the school register and absences recorded with reconciliation with COVID-19 associated absences. This will be compared between study arms, to historic schools' data, and to national schools' benchmark data collected via a survey of non-participating schools.

(ii) Estimated number of in-school COVID-19 transmission events

The number of positive cases will be obtained from the following sources:

- 1. Weekly LFD active case finding (Control and Intervention Arms)
- 2. Symptomatic individuals' NHS Test and Trace results obtained from Community Testing routine data (Control and Intervention Arms)
- 3. In-school LFD DCT testing (Interventional Arm).

Positivity rates will be reported for each source separately to facilitate like-for-like comparison between arms

Epidemiological links between cases will be obtained from the NHS Test & Trace Contact Tracing and Advice Service data base. Additional links will be obtained by membership of school-reported contact groups. Onward transmission from the index case will be determined by the following:

• Genomic sequence of virus: The additional PCR swab collected from positive individuals will be used to determine the whole genomic sequence of isolates. A sample of apparent links will be assessed with comparisons of whole genome sequencing. The diversity of genetic sequences both in the schools and the

community (routinely determined by COG) will be used to help interpret the results. Preliminary work currently undertaken will determine the appropriate genetic distance to be used to exclude a direct transmission event between individuals. This is likely to be 2 SNPs.

- Plausible epidemiological link (e.g. membership of same close contact group)
- For positive individuals identified in DCT the DMIC will review all available data to determine if the individual's infection was likely to have resulted from onward transmission from the index case, or via co-infection from an unknown 'upstream' positive or out-of-school positive case.

Secondary End-Points

(iii) Number of positive first-order contacts missed by daily LFD testing (Intervention arm only).

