Routine qPCR of first-order contacts will be used to determine the performance of DCT testing with LFDs. Comparisons of PCR with the same day LFD will allow comparison between CT values and LFD results in a 'real world setting' These comparisons can also be used to compare the relative performance between assisted school-based testing and home/self-testing.

(iv) Number of COVID-19 cases transmitted to the first-order contacts of index cases ("primary attack rate").

The first-order close contacts of all index cases will be identified by the school based on their existing close contact management policy. LFD DCT testing and (for symptomatic individuals) routine NHS Test and Trace PCR testing will be used to calculate primary attack rate.

As above, genomic sequencing will be used, wherever possible, to exclude non-direct transmission events.

(v) Number of COVID-19 cases transmitted to the second-order contacts of index cases ("secondary attack rate").

The second-order contacts of all index cases will be identified (regardless of the COVID-19 status of the DCT-contacts) as described in Section 3.7. The COVID-19 status of these second-order contacts will be measured in two ways:

- i. Where the second-order contact is a consented participant in this study their COVID-19 status will be assessed by weekly LFD active case finding, and records kept by the school of any participants who become symptomatic and test positive via standard NHS Test and Trace community testing.
- ii. Where the second-order contact is not a consented participant in this study (e.g., household contact of first-order contact), analysis of routine NHS Test and Trace data will be used to determine if they subsequently become symptomatic and test positive in the community setting.

As above, genomic sequencing will be used, wherever possible, to exclude non-direct transmission events.

(vi) Number and proportion of school attendees testing COVID-19 positive in weekly active case finding.

LFD results and school attendance registers will be used to calculate active case finding rate. This will be compared between study arms, and to national schools' benchmark data collected via a survey of non-participating schools.

(vii) Proportion of student and staff who accept an offer of weekly active case finding testing with LFD devices.

Schools will maintain consenting records to allow participation rates to be calculated.

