4.6 Multiple Positive Cases in a School

The management of local outbreaks in a school will be managed according to the exiting national process. The school will contact the DfE coronavirus helpline ([contact] / [name]) for initial risk assessment and this will be escalated to PHE Health Protection Teams for advice managing large or complex outbreaks. The study team will also be notified. If the HPT, DPH or the school wants to stop the trial and instruct a contact group to self-isolate they should discuss this with the Trial Steering Committee. The Trial might be able to provide extra genomic analysis to determine the extent of the outbreak and help inform decision making. If DCT is stopped the IDMC should be informed.

¹⁴ COVID-19: guidance for households with possible coronavirus infection - GOV.UK (www.gov.uk)

¹⁵ https://www.gov.uk/get-coronavirus-test

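### The transmission co-primary compares sequences for only an unspecified sample of links, so any sequence-refined event count depends on the share compared

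*Protocol*

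**What the plan says.** Section 3.6 determines onward transmission for co-primary (ii) from three things: viral sequence, a plausible epidemiological link, and a committee review. It does not say how they combine.

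- **Swabs.** Section 3.1: "All individuals with a positive test will be asked to provide a PCR swab test for genomic sequencing". Section 3.6: "The additional PCR swab collected from positive individuals will be used to determine the whole genomic sequence of isolates".
- **Coverage of links.** The next sentence in 3.6: "A sample of apparent links will be assessed with comparisons of whole genome sequencing". No fraction, selection rule or balance between arms follows.
- **Direction of the rule in 3.6.** Sequencing removes links: "Preliminary work currently undertaken will determine the appropriate genetic distance to be used to exclude a direct transmission event between individuals". The threshold is expected to be 2 SNPs.
- **Review.** "For positive individuals identified in DCT the DMIC will review all available data to determine if the individual's infection was likely to have resulted" from the index case or from another source. No equivalent is stated for control-arm cases.
- **Secondary end-points (iv) and (v).** The text refers back to the method above and says "genomic sequencing will be used, wherever possible, to exclude non-direct transmission events".
- **Outbreaks.** Section 4.6: "The Trial might be able to provide extra genomic analysis to determine the extent of the outbreak and help inform decision making".
- **Analysis measures.** The statistical analysis text in section 5.3 sets two. Unadjusted events are all positive cases from Pillar 2 and school-directed testing. Events are then classed as *more likely* if they have a similar sequence or belong to the same predefined bubble.

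**The concern.** Sequencing is the trial's main objective tool for separating in-school transmission from coincident infection. Every positive is asked for a swab and the swabs are to be sequenced, yet the co-primary carries a looser stated comparison rule than two secondary end-points. If the links compared are chosen by convenience, laboratory capacity or outbreak size, the refined count reflects that choice as well as transmission.

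The stakes come from section 3.9. It sets no non-inferiority margin for transmission. If attendance shows superiority, an independent committee judges whether the 95% confidence interval for the difference in transmission is close enough to no difference. A shift in the estimate caused by uneven comparison would feed directly into that judgement.

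**Working it through.** **Inputs.** The protocol gives no event rate, margin or power for transmission, so it has no figure of its own to reproduce. Two quantities are needed and neither is stated:

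- *s*, the share of apparent links compared by sequence (assumed, 0 to 1);
- *f*, the share of apparent links that a comparison would exclude (assumed, 0.1 to 0.6).

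**Step 1. Count under the exclusion rule of 3.6.** Suppose, for illustration, that links not compared are kept on their epidemiological link. Then count = L × (1 − s·f). With L = 100:

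| f | s = 0 | s = 0.5 | s = 1 |
|---|---|---|---|
| 0.1 | 100 | 95 | 90 |
| 0.3 | 100 | 85 | 70 |
| 0.5 | 100 | 75 | 50 |

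**Step 2. Ratio between arms, equal links and equal *f*, so the true ratio is 1.** Ratio (DCT/control) = (1 − s_DCT·f)/(1 − s_control·f).

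- Both arms at s = 0.5: 1.00 for any f.
- DCT 0.75, control 0.25: 0.925/0.975 = 0.95 (f = 0.1); 0.775/0.925 = 0.84 (f = 0.3); 0.625/0.875 = 0.71 (f = 0.5).
- DCT 0.25, control 0.75: 1.05, 1.19 and 1.40 for the same f.
- DCT 0.4, control 0.8: 0.92/0.84 = 1.10 (f = 0.2); 0.84/0.68 = 1.24 (f = 0.4); 0.76/0.52 = 1.46 (f = 0.6).

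**Step 3. Equal *s*, different *f*.** With equal links, f = 0.1 in DCT and 0.3 in control, the ratio is 1.00 at s = 0, 0.95/0.85 = 1.12 at s = 0.5 and 0.90/0.70 = 1.29 at s = 1. Full comparison gives 1.29; anything less pulls the ratio towards 1.00. Equal sampling without weighting therefore does not fully protect the contrast.

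**Step 4. Count under the inclusion rule of 5.3.** Let B be same-bubble links, O other links, and p the share of O with a similar sequence. *More likely* count = B + s·O·p. With assumed B = 80, O = 20 and p = 0.5, this is 80, 85 and 90 at s = 0, 0.5 and 1. At s = 0.75 against 0.25 the ratio is 87.5/82.5 = 1.06. More sequencing now raises the count, the opposite of Step 1, and a same-bubble pair stays in even if its sequences differ.

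**Step 5. Unadjusted measure in 5.3.** All positive cases are counted, so the result is the same for every s.

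**The case against.** A reader might infer that every link outside the sample is counted as transmission, and that the DCT count is therefore inflated. The documents do not support this:

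- No sentence says that links not compared stay counted. The end-point is an estimated number, which is compatible with applying the confirmed fraction from the sample to the rest.
- DCT positives are reviewed on all available data, so their uncompared links are not accepted automatically.
- Section 3.9 does expect more outbreaks detected under DCT (2 against 1 per month in Table 1), but no fixed sequencing budget is stated. More links need not mean a smaller share compared.
- The extra genomic work in 4.6 is conditional, open to either arm, and not said to feed the end-point.
- The 5.3 measures do not follow the formula in Step 1: one ignores sequencing and the other moves the opposite way.

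All of this stands, and it removes any claim to a known direction or size. It can also be said that (iv) and (v) refer back to the same procedure, and that sampling detail often sits in a statistical analysis plan. That is fair for weights and probabilities. It does not explain why the protocol's own text limits the co-primary to a sample while two secondaries use sequencing wherever possible, nor why 3.6 and 5.3 use sequence in opposite directions.

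**Conclusion.** The point holds in a limited form. Section 3.6 restricts sequence comparison for co-primary (ii) to a sample with no rule, so any sequence-refined count depends on the share compared, whether sequence excludes links (3.6) or adds them (5.3). Bias between arms is possible, not shown: it needs the share compared or the false-link share to differ by arm. With both equal, the Step 2 ratio is 1.00. The range of about 0.7 to 1.5 rests wholly on assumed shares, on equal numbers of links, and on keeping links that were not compared. The unadjusted all-cases measure is untouched, but it counts infections rather than in-school transmission. The review of DCT positives alone is a further unevenness between arms.

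**What to change.** 1. Replace the sampling sentence in 3.6 (ii): every apparent link for which both sequences exist is compared, in both arms.
2. If laboratory capacity forces sampling, draw links at random with the same probability in each arm and weight by the inverse of that probability.
3. Say how links without both sequences enter the estimate, for example at the fraction confirmed among compared links of the same arm and link type.
4. Keep sequencing triggered by outbreaks under 4.6 out of this estimate.
5. Reconcile 3.6 with 5.3 so that one case definition, with one stated role for sequence, bubble membership and case review, applies alike in both arms.

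The cost is wording and some analysis work. Section 3.6 already plans to sequence the swabs, so comparing those sequences adds little. The small downside is an extra variance term for links without sequences. The rule should be settled before sequencing is allocated.

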Appendix 4 – Terms of Reference for Independent Data Monitoring Committee (IDMC)

The role of the IDMC

The IDMC's main role is as follows:

- It is the only body involved in the trial that has access to the unblinded comparative data
- The role of its members is to monitor these data and make recommendations to the Trial Steering Committee (TSC) on whether there is there evidence beyond reasonable doubt that one arm is superior to another arm such that it is likely to change public health or educational practice.
- The safety, rights and well-being of the trial participants are paramount
- The IDMC considers the need for any interim analysis advising the TSC regarding the release of data and/or information
- The IDMC may be asked by the ISSG to consider data emerging from other related studies
- There are also rare occasions when the IDMC chair might be asked, by the chair of the TSC to provide advice based on a confidential interim or futility analysis if serious concerns are raised about the viability of the study or if the research team are requesting significant extensions.
- Criteria should be agreed at which continuation of the trial is considered futile and the DM(E)C would only indicate if these had been passed or not as this would limit the potential for un-blinding.

Constitution of the IDMC

- Members of the IDMC will be appointed by the Department of Health and Social Care and the Department for Education
- Only appointed members will be entitled to vote, and the Chair will have a casting vote
- The minimum quoracy for a meeting to conduct business is 67% (two thirds) of appointed members
- The Chair and members must sign and maintain a log of potential conflicts and/or interests
- Attendance at IDMC meetings by non-members is at the discretion of the Chair
- The primary IDMC reporting line is via the Chair to the TSC.

Composition Requirements of the IDMC

- All IDMC members are to be independent*
- Membership of the IDMC will be four members, comprising experts in the field, e.g. a clinician with experience in infectious disease epidemiology, an expert in working with educational settings and an expert trial statistician.
IDMC Meetings

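### A source-attribution review that can take transmission events out of the count is prescribed only for positives found by daily contact testing, who exist only in the intervention arm, and section 5.3 does not say whether it enters the co-primary analysis

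*Protocol*

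**What the plan says.** Section 2.1 makes within-school transmission a co-primary endpoint. Section 3.6(ii) names three sources of cases: weekly lateral flow testing and symptomatic Test and Trace results in both arms, and in-school DCT testing in the intervention arm only. It then gives three determinants of onward transmission.

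- **Sequence.** Section 3.1 covers both arms: "All individuals with a positive test will be asked to provide a PCR swab test for genomic sequencing". Section 3.6 says preliminary work "will determine the appropriate genetic distance to be used to exclude a direct transmission event between individuals". It also says: "A sample of apparent links will be assessed with comparisons of whole genome sequencing". The fraction is not given.
- **Epidemiological link.** The example is shared membership of a close contact group. No arm is specified.
- **Case review.** "For positive individuals identified in DCT the DMIC will review all available data", to judge whether the infection came from the index case "or via co-infection from an unknown 'upstream' positive or out-of-school positive case".

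Section 5.3 sets out the analysis. It defines an unadjusted count (all positive cases) and a 'more likely' category (similar sequence, or same predefined bubble). Neither mentions the case review.

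DMIC is not defined and occurs nowhere else in the text available. The nearest name is the IDMC, of which Appendix 4 says: "It is the only body involved in the trial that has access to the unblinded comparative data". Section 5.3 gives that access to the statistical centre as well.

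**The concern.** Whether a positive contact counts as a transmission event should depend on the evidence about that contact, not on the arm. Here a judgement-based step that can move a case out of the count is prescribed for one detection route, and that route exists in one arm. A DCT-detected case also reveals its arm to whoever reviews it.

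The comparison is exposed to this. Section 3.9 sets no non-inferiority margin for transmission and asks an independent committee to judge whether the 95% confidence interval lies close enough to no difference. Any shift caused by differential classification passes straight into that judgement.

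**Working it through.** **1. Can the case review add events, or only remove them?** Section 4.2.1 offers DCT to the index case's first-order close contact group. Every DCT positive therefore already satisfies the link example in section 3.6. The open question for the reviewers is whether another source overrides that link. The outcome is confirmation or removal.

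**2. Like cases compared.** Take two contacts, each in the close contact group of an index case, each later positive, neither link among those sequenced.

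| | Intervention, found by DCT | Control, found by Test and Trace |
|---|---|---|
| Link rule | met | met |
| Sequence comparison | none (not sampled) | none (not sampled) |
| Case review | yes, may be removed | none described |

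**3. Number of cases reviewable.** Inputs from section 3.9: 50 schools per arm, a two-month study, 35 of 50 contacts in DCT, and 5% of them positive. 35 × 0.05 = 1.75, which the protocol rounds to about 2. For index cases in the intervention arm, the prose says 2 per week and Table 1 says 2 per month. Table 2 supports the monthly figure. With 4 index cases per school over two months and 15 + 3 = 18 pupils isolating per index case, against 2 index cases and 51 pupils in control:

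n = (1.96 + 0.84)² × (2×51² + 4×18²) / (2×51 − 4×18)² = 7.85 × 6498 / 900 ≈ 57, against 58 printed.

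Reviewable positives, at about 2 per index case:

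- at 1 index case per month (the control rate, as a lower bound): 50 × 2 × 1 × 2 = 200
- at 2 per month: 50 × 2 × 2 × 2 = 400
- control arm: 0

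**4. Effect of the step on the rate ratio.** Let both arms have E true linked events. Let d be the share of intervention events found by DCT and q the share of those that the case review removes. The intervention count is E − d×q×E and the control count is E, so the counted ratio is 1 − d×q. Neither d nor q is in the protocol; the values below are assumptions.

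| d | q = 0.10 | q = 0.30 |
|---|---|---|
| 0.25 | 0.975 | 0.925 |
| 0.50 | 0.95 | 0.85 |
| 0.75 | 0.925 | 0.775 |
| 1 (ceiling) | 0.90 | 0.70 |

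**5. The opposing effect.** Suppose DCT raises the number of linked positives detected in the intervention arm by a proportion a, with no matching source in control. The counted ratio becomes (1 + a)(1 − d×q), which returns to 1 when a = d×q / (1 − d×q). For d = 0.5 and q = 0.10 to 0.30, that is 0.05/0.95 = 0.053 to 0.15/0.85 = 0.176. Extra detection of about 5% to 18% would cancel the step, and more would reverse the net direction.

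**6. Sections 3.6 and 5.3 side by side.** The definitions at the front of the protocol make first-order contacts a subset of a bubble. A DCT positive whom the case review attributes to an outside source is therefore not onward transmission under section 3.6. The same person still falls in the 'more likely' category under section 5.3 through bubble membership, and is also in the unadjusted count. The two sections give different answers for the same case.

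**The case against.** The strongest reply is that the case review may never reach the co-primary analysis. Neither count in section 5.3 uses it, so those counts lose no event through it. That stands as a limit on what can be claimed. It does not settle the matter, because section 3.6 says the case review helps determine the endpoint and section 5.3 does not withdraw this.

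A reader might also infer more than the protocol supports:

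- **That the transmission comparison as a whole is biased toward non-inferiority.** Only the step, taken alone, pushes that way. DCT is also an extra case-finding source in the intervention arm, and scrutiny of those additional positives may partly offset it. Section 3.6 plans to report positivity by source for like-for-like comparison. But an unmasked override of unknown size is not a calibrated correction for extra detection.
- **That events can leave one arm only.** This is true of the case review, not of the endpoint. The sequence rule can exclude direct transmission in either arm, though only for the links sampled. Some cases the review would remove would fail the sequence rule anyway. The review also follows detection route: intervention contacts who decline DCT are not reviewed either.
- **That the ratio falls by 10% to 30%, to be set against the 50% relative increase mentioned in section 3.9.** With q in that range, such a fall requires every counted intervention event to be a DCT positive, and section 3.6 lists two other sources. The 50% is a hypothetical at a 20% control rate, not a margin.
- **That the unblinded monitoring committee adjudicates its own endpoint.** DMIC may be a transposition of IDMC, but the protocol does not say so, and case adjudication is not among the IDMC duties in section 5.3 or Appendix 4. The membership lists that section 3.10 places in Appendix 6 were not available to check.

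Masking procedure may reasonably sit in a charter or the SAP. The restriction of the case review to one arm's cases is stated in the protocol itself.

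**Conclusion.** The concern holds as a flaw in how the endpoint is determined. For a co-primary endpoint, section 3.6(ii) prescribes a judgement that can only confirm or remove events and confines it to cases that arise in one arm, while section 5.3 leaves open whether it counts.

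If it does count, the step alone multiplies the rate ratio by 1 − d×q: 0.95 to 0.85 for d = 0.5 and q = 0.10 to 0.30, on assumed values. About 200 to 400 intervention positives would be open to the case review against none in control, on the section 3.9 assumptions. The net direction of bias in the full comparison is not established. The identity of the reviewing body is unresolved, and the need for correction does not depend on it.

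**What to change.** Choose one of two options.

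- **Drop the DCT-only case review** and apply the same sequence and link rule to every positive first-order contact in both arms. The cost is wording only.
- **Keep a case review, but run it on positive first-order contacts in both arms**, masked to arm as far as possible, by a named group separate from the IDMC. The cost is preparing case summaries for control positives. Masking will be imperfect, since test timing and school attendance can reveal the arm.

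Under either option, define DMIC or remove the term, and reconcile sections 3.6 and 5.3 so that one rule defines the co-primary transmission count.
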